10.1.3.2. Blood Loss

As defined in Section 10.3.3.2.1, the measure of blood loss per patient will be computed using two different methods:

- Method 1: treating the whole eschar removal process as one continuous procedure
- Method 2: summing the blood loss computed per procedure over all procedures carried out to remove eschar

Missing blood loss values will be imputed separately for each method. The procedures can be described as follows:

1. Test for normality:

- For Method 1: The measure of blood loss defined in Section 10.3.3.2.1 will be computed for each patient.
- For Method 2: The measure of blood loss defined in Section 7.2.2.210.3.3.2.1
 will be computed for each procedure and aggregated to patient level.

An ANOVA model (on a patient level) incorporating the stratification factors treatment center, %TBSA, proportion of the FT area and age will be used to detect differences between both treatment groups. The normality of the data will be tested on residuals of this model using the Shapiro-Wilk test. If the normal distribution hypothesis is not rejected at the 5% significance level, then the ANOVA model will constitute the main analysis model. In case the normal distribution hypothesis is rejected at the 5% significance level, then a stratified Wilcoxon test, using the same stratification variables as outlined for the ANOVA, will be used.

2. Imputation:

If the normality condition is satisfied, the following will be performed:

- For Method 1: Fit a linear regression model with target variable blood loss on a
 patient level (as computed in Section 10.3.3.2.1) and independent variables
 age, wound area, depth of wound (categorized as all DPT / mixed / all FT) and
 course of debridement procedure (as defined in Section 10.3.3.2.5) to the
 subset containing patients with complete data in those variables for both
 treatment groups separately.

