- For Method 2: Fit a linear regression model with target variable blood loss on a procedure level (as computed in Section 10.3.3.2) and independent variables age, size of wounds treated in this procedure (wound area), proportion of area SPT of wounds treated in this procedure (as defined in Section 10.3.3.2.2), proportion of area DPT of wounds treated in this procedure (as defined in Section 10.3.3.2.3), proportion of area FT of wounds treated in this procedure (as defined in Section 10.3.3.2.4) and type of procedure (surgical/non-surgical) to the subset containing patients with complete data in those variables for both treatment groups separately. This model will treat all the procedures as independent.

Impute the missing entries of the incomplete data sets m = 25 times as follows. Draw a set of regression coefficients from their sampling distribution obtained from fitting the respective linear models outlined above. Sample a variance as the quotient between the residual variance from the linear model fitted to the data and a random variable which is chi-square distributed with corresponding degrees of freedom (a different distribution for the regression coefficients and variance will be obtained in the different treatment groups). With these sampled coefficients calculate the predicted blood loss values for the missing blood loss values using the covariate information. To these predicted blood loss values add the realizations of a normally distributed random variable with zero mean and standard deviation equal to the sampled standard deviation. The imputation outlined above will be performed using PROC MI in SAS. If the normality condition is not satisfied, then the multiple imputation method known as predictive mean matching will be used. Random draws from the five nearest neighbors for each missing value, and m=25 multiply imputed datasets will be used. The predictive mean matching method is implemented in the SAS procedure PROC MI.

- For Method 1: The random seed will be 12467.
- For Method 2: The random seed will be 1732. On the imputed datasets the blood loss on a patient level will be calculated.

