- 3. Analysis: Analyze each of the m complete datasets with an ANOVA or the stratified Wilcoxon test according to the test result in step 1 using the re-randomization test outlined in Section 11.1.2. An estimated treatment difference, δ (NexoBrid versus SoC), from the analysis model and a two-sided p-value, p, from the permutation test (as described in Section 11.1.2) will be obtained for each imputed dataset. In case the analysis is performed with the stratified Wilcoxon test, Hodges-Lehmann (HL) estimate for treatment difference will be used (options ALIGN=STRATA WILCOXON HL in SAS NPAR1WAY procedure).
- 4. Pooling: Integrate the m analysis results into a final result, as follows. A "working standard error", s, of the estimated treatment difference for each imputed dataset will be obtained by $s = \delta/\Phi^{-1}(1-p/2)$ if $\delta>0$, or $s = \delta/\Phi^{-1}(p/2)$ if $\delta<0$, where Φ^{-1} is the inverse of the standard normal cumulative distribution function. Then Rubin's rules will be used to combine the set of values of δ and s (using PROC MIANALYZE in SAS) to give an overall estimate of δ and its standard error.

- 5. The p-values (p_{1, ...,} p_m) will be combined using the Licht-Rubin formula (as described in Section 4.1 of [16]), as follows:
 - 1) Compute $z_i = \Phi^{-1}(1-p_i)$ for each i
 - 2) Compute the mean: $\bar{z} = \frac{1}{m} \sum_{i=1}^{m} z_i$
 - 3) Compute the between variance: B = $\frac{1}{m-1}\sum_{i=1}(z_i-\bar{z})^2$
 - 4) Compute the total variance: $T = 1 + (1 + m^{-1})B$
 - 5) Compute the relative variance increase due to non-response: $r = (1 + m^{-1})B$
 - 6) Compute the degrees of freedom: $v = (m-1)(1+r^{-1})^2$
 - 7) The final p-value is then: $\Pr[t_{\nu} > \overline{z}/\sqrt{T}]$ where t_{ν} is the t-distribution with ν degrees of freedom.

Analyses with both blood loss values will be conducted. However, the analysis with less missing values will be regarded as more reliable and is therefore considered the main analysis. The other analysis is considered supportive.

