10.3.3.2. Blood Loss

10.3.3.2.1. Blood Loss Calculation

Blood loss will be calculated using the following formula [15], [48]:

$$Blood\ Loss\ (mL) = \frac{RBCV_{before} + (Transfusion\ RBCV) - RBCV_{after}}{Hct_{after} [\%] * 0.01}$$

RBCV (mL) = Red Blood Cell Volume (mL) = Body Weight (kg) * 80 (mL/kg) * (Hematocrit [%] * 0.01)

Transfusion RBCV (mL) = [Total Volume (mL) of Whole Blood Transfused * 0.3] + [Total Volume (mL) of Packed Red Blood Cells Transfused * 0.8]

The blood loss will be computed over the whole eschar removal period, using the formula above, i.e. the eschar removal process will be considered as one continuous procedure. Therefore, only the Hematocrit value before the first eschar removal procedure and after the last procedure will be used and all blood transfusions performed between these measurements will be included.

Additionally, the blood loss will be summed over all procedures carried out to remove eschar, with the hematocrit measured immediately before each procedure and 4 hours after its completion. The amount of blood transfused will be summed over all transfusions carried out during the debridement procedure and up to 24 hours from the end time of the debridement procedure.

Analyses with both blood loss values will be conducted. However, some missing values are expected. The analysis with less missing values will be regarded as more reliable and is therefore considered the main analysis. The other analysis is considered supportive.

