11.1.2. Re-Randomization Test

Treatment allocation will be performed in this trial by minimization, therefore the p-values reported in this trial for the main analyses of the primary and secondary endpoints, performed on the FAS, will be based on the re-randomization test. To note, all other analyses (sensitivity, supportive, additional), including analyses on PP population, will be performed without the rerandomization test.

The re-randomization test is advocated by Proschan et al (Biometrics 2011; 67:1135-41) for trials that employ minimization, and belongs to the class of tests that are based on permuting the treatment allocations of the patients.

The test works as follows. Suppose the analysis for an endpoint is performed as described in Sections 11.1.3 or 11.1.4 below and a p-value for the estimated treatment difference is p*. We now return to the list of patients in the same order as they entered the trial and re-apply the minimization procedure to their treatment allocation, as described in Appendix 13.1. Because

the procedure involves random allocations at various junctures during the trial, the next time we apply the procedure it will in general yield a different set of treatment allocations for the patients. Having obtained these new treatment allocations, we then re-analyze the data as if these had been the true treatment allocations, and obtain a new p-value p_1 and corresponding test statistic s_1 for the test of the treatment difference. We repeat this step a large number of times (in this trial we will use 8000 repeats) and obtain a set of 8000 pairs of p-values and test statistics (p_1 , s_1), (p_2 , s_2), ..., (p_{8000} , s_{8000}). If exactly n of these 8000 p-values are less than or equal to the value p^* (obtained on the real data) with the test statistic in the direction of advantage to NexoBrid, then the re-randomization test p-value is assigned the value 2*n/8000.

The random seed for the re-randomization will be 48920.

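### Blood loss: the re-randomization p-value can be exactly 0 in an imputed dataset, and the planned pooled p-value and standard error then cannot be computed as written

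*SAP*

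**What the plan says.** SAP 11.1.2 regenerates the minimization allocation 8000 times. It counts the n re-runs whose p-value is no larger than the real one, with the statistic favoring NexoBrid, and "then the re-randomization test p-value is assigned the value 2*n/8000".

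For blood loss, SAP 10.3.3.2.1 warns of gaps in the data ("However, some missing values are expected"), and 13.3 plans for 30% missing. SAP 10.1.3.2 therefore imputes 25 times and analyzes each dataset with the re-randomization test:

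- **Branch.** ANOVA is the default. "In case the normal distribution hypothesis is rejected at the 5% significance level, then a stratified Wilcoxon test" replaces it, with predictive mean matching ("Random draws from the five nearest neighbors for each missing value") and a Hodges-Lehmann estimate ("options ALIGN=STRATA WILCOXON HL in SAS NPAR1WAY procedure").
- **Item 4.** A working standard error s "of the estimated treatment difference for each imputed dataset will be obtained by" dividing the difference δ by Φ⁻¹(1−p/2) if δ > 0, or by Φ⁻¹(p/2) if δ < 0. Rubin's rules follow.
- **Item 5.** The 25 p-values "will be combined using the Licht-Rubin formula", starting from z_i = Φ⁻¹(1−p_i). Step 6 ("Compute the degrees of freedom") uses (m−1)(1+1/r)².

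SAP 10.1.3.3 item 3 sends area of autograft in DPT wounds through the same items 4 and 5. Neither document says what to do if n = 0, if n ≥ 4000 or if the between-imputation variance B is 0.

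**The concern.** A Monte Carlo p-value should count the observed allocation among the possible ones; otherwise it can equal 0, which is not a valid p-value. For an endpoint analyzed once, such as the primary, that is only a reporting flaw. For blood loss the p-value is an input to further formulas, and Φ⁻¹ is not finite at 0 or 1. One n = 0 among 25 datasets therefore stops the pooling.

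Blood loss is step 3 of the hierarchy in SAP 11.1.9, and SAP 11.1.4.2 promises an estimate, a standard error and a combined p-value. Unless a dry run exposes the gap first, someone would have to choose a convention after seeing the data.

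**Working it through.** **1. Inputs and the plan's own figure.** The documents give no SD for blood loss. Solving the 13.3 figure for MW2004-11-02 (173 per group, 90% power, 468.47 mL) gives an SD of about 1340 mL. With 80 per group and 465.54 mL (the blood-loss power paragraph in SAP 9.1), the noncentral t gives power 0.588, which matches the stated 58.8%. For MW2010-03-02 (28 per group, 722.30 mL) the SD is about 819 mL.

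The stated standard error of 156.08 for MW2010-03-02 does not follow from its arm values: √(66.15² + 167.74²) = 180.3. The MW2004-11-02 value does: √(129.52² + 240.98²) = 273.58. A third scenario therefore uses 800.34 − 180.3/2 = 710.19 mL and SD 819 × 180.3/156.08 = 946 mL.

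**2. Item 5 with one p_i = 0.** Then z_i = Φ⁻¹(1) = ∞ and the mean z is ∞. B contains ∞ − ∞, so B, T, r, the degrees of freedom and p are all undefined. With p ≥ 1 (n ≥ 4000), z_i is −∞ or undefined; for example n = 4500 gives p = 1.125 and Φ⁻¹(−0.125).

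**3. Item 4.** At p = 0 the argument is 1 (δ > 0) or 0 (δ < 0), so Φ⁻¹ is infinite. At p = 1, Φ⁻¹(0.5) = 0 and s divides by zero. At p > 1, s is negative.

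**4. Chance of n = 0 in one dataset.** P(n=0) = E[(1−q)^8000], where q is the upper tail of Z ~ N(ncp, 1) and ncp = δ/(SD·√(2/72.5)) for 145 patients.

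- MW2004-11-02: 465.54/222.6 = 2.09, giving 5% (2.5% with 30% fewer evaluable).
- MW2010-03-02: 722.30/136.0 = 5.31, giving 93% (73% with 30% fewer).
- No effect: about 1 in 8000.

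**5. Chance over 25 datasets.** The simulation used 1200 trials per setting, 145 patients with the age split in 13.3, Appendix 13.1 minimization, 8000 re-runs, Shapiro-Wilk branch choice and 25 imputations by arm. Pairs are for 10% / 30% missing.

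| Effect | Any n = 0, normal errors (mostly ANOVA) | Any n = 0, data mostly triggering Wilcoxon | Item 5 not computable (n = 0 or n ≥ 4000) | All 25 at n = 0 |
|---|---|---|---|---|
| MW2004-11-02 | 14% / 37% | 2–7% / 11–22% | 8–39% | at most 0.6% |
| MW2010-03-02, SE 156.08 | 96% / 98% | 78–91% / 90–97% | 78–98% | 12–59% |
| MW2010-03-02, SE 180.3 | 87% / 93% | 59–65% / 76–81% | 59–93% | 5–32% |

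The Monte Carlo standard error is at most 1.5 points. A normal approximation with a between-imputation SD of z of 0.3 to 0.6 gives 10–32%, 92–99.9% and 76–99% for any n = 0 in the three rows. A van Elteren form of the Wilcoxon test gives figures 1 to 12 points lower.

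**6. After adding one.** The smallest p is 2/8001 = 0.00025, so z_i = 3.48. With counts n = 0, 1, …, 24 across the 25 datasets, mean z = 2.79, B = 0.067, T = 1.070 and pooled p = 0.0035; the same counts under 2n/8000 give no result. If all 25 have n = 0, every z_i is equal, B = r = 0, and step 6 divides by zero. Add-one alone is therefore not quite enough.

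**The case against.** The strongest reply is that this hardly affects the conclusion. A count of 0 arises only when a dataset separates the arms strongly. In a normal-approximation check, trials with any n = 0 were significant after add-one in 91% to 100% of cases, and add-one and a half-count convention disagreed at 0.05 in at most 0.33%. In the simulation, three candidate conventions disagreed in 0% to 2.9% of affected trials. Double programming (SAP 6.4) would expose an infinite z. All of this stands, but exposing the failure does not supply a pre-specified rule.

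The standard error in item 4 could also be read as its limit, s = 0, and Rubin's rules would then return a number. That is true, but such a dataset contributes no within-imputation variance, so the result is degenerate.

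The frequencies are soft, and this stands too. The simulation imputed on age, %TBSA and depth, without course of debridement, and did not simulate Method 2, which becomes the main analysis if it has fewer missing values. MW2010-03-02 was an adult study with a different blood-loss formula. These points affect how often the failure occurs, not whether it does.

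Finally, SAP 10.1.3.3 expects very few missing values and SAP 9.1 puts power for area of autograft at 23.1%, so the failure is much less likely there.

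**Conclusion.** The concern holds. The p-value rule in SAP 11.1.2 and the pooling rules in SAP 10.1.3.2 do not work together as written, and this follows from the formulas alone. One n = 0 in 25 datasets is enough. It should be fixed, because it concerns a confirmatory step and the repair is nearly free.

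How often it happens depends on the effect: 2% to 37% of trials under MW2004-11-02, and 59% to 98% under MW2010-03-02, which is the upper scenario. These figures rest on assumptions not in the documents:

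- 30 centers in four regions, assumed TBSA and FT distributions, and the first 0 or 40 patients under strict minimization;
- data missing at random, at 10% or 30%;
- errors either normal with equal SD, or exponential with unequal arm SDs, and loss either scaled or not scaled by body weight.

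The loss is a pre-specified p-value and standard error, seldom a different test decision.

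**What to change.** 1. **SAP 11.1.2:** define p = 2(n+1)/8001, capped at 8000/8001.
2. **SAP 10.1.3.2 item 5:** add that if B = 0, then r = 0, the degrees of freedom are infinite and the final p comes from the standard normal distribution. If all 25 datasets have n = 0, this gives mean z 3.48 and p 0.00025.
3. **SAP 10.1.3.2 item 4, preferred:** take s for each imputed dataset from the analysis model (the ANOVA or regression standard error, or the asymptotic standard error of the Hodges-Lehmann estimate). If s is still solved from p, every n = 0 dataset gets |δ|/3.66 whatever its precision, and a dataset at the cap gets about 6,400 × |δ|.

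Changes 1 and 2 suffice for the p-value: item 5 was finite in all 28,800 simulated analyses. SAP 10.1.3.3 item 3 inherits the changes.

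The cost is one formula and one or two sentences, with no extra re-randomization runs. The smallest reportable p becomes 0.00025. Where the written rule also gives an answer, add-one changed the 0.05 decision in 9 of 11,115 simulated analyses. Change 3 unties the standard error from the re-randomization p-value. In affected trials with add-one, the median p-derived pooled standard error was 4–6% (MW2004-11-02) or 19–40% (MW2010-03-02) above the model-based one under normal errors, and 0–14% below it where the Wilcoxon branch dominated.

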11.1.3. Primary Efficacy Analysis: Time to Complete Eschar Removal

The primary efficacy variable will be analyzed using the FAS. Missing data for the main primary analysis and for the three sensitivity analyses will be handled by the methods described in Section 10.1.2. In addition, the primary analysis will be repeated for the PP collective as sensitivity analysis.

Time until complete eschar removal will be defined as the time until complete eschar removal has been achieved for all TWs. This will be measured as time from the randomization date (days). Kaplan-Meier curves will be presented graphically to display the distribution of time to complete eschar removal under the two treatments. Median time to complete eschar removal

will be estimated for each treatment group with a 95% confidence interval. Furthermore, descriptive statistics for time to complete eschar removal will be presented. The treatment groups will be compared using a Cox regression model. The comparison will be adjusted for clinical center, age, %TBSA, proportion of the FT area of a patient and number of TWs (1,2,3-4, ≥5) by including each of them in the Cox regression model together with the treatment variable (NexoBrid vs. SoC). The treatment groups will be compared by testing the null hypothesis of no difference, comparing the ratio of the estimated treatment coefficient to its standard error to a standard normal distribution.

The Cox Regression analysis outlined above will be performed if the proportional hazards assumption appears to hold. This will be checked by including in the regression model a variable representing the interaction between time since randomization and treatment group. This coefficient will be tested (on actual sample allocation, without the re-randomization test) to be nonzero. Additionally, a log likelihood test comparing the model fit of a model with all time by covariate interactions added with a model without these interactions will be computed. The proportionality assumption will be rejected if one of these tests yields a significant result at the 10% level. In this case, we will use a generalized Wilcoxon-Gehan test. The Wilcoxon-Gehan test will be performed using the Wilcoxon option (also provided by default) in the SAS procedure PROC LIFETEST using the following SAS Code:

```
PROC LIFETEST DATA=burn_data;
TIME time*status(0);
STRATA agegroup ftgroup numtw tbsagroup centergroup / GROUP = treatment_group;
RUN;
```

Here burn_data is the data set containing all necessary information. The variable time is the time to complete eschar removal, status is a censoring variable (0 for censor and 1 for complete ER event) and agegroup, ftgroup, numtw, tbsagroup, and centergroup are the variables, which the model is adjusted for. Agegroup, ftgroup, tbsagroup and centergroup are the stratification levels defined in Section 11.1.11 and numtw is the number of target wounds $(1, 2, 3-4, \ge 5)$.

Supportive analyses will include adjustment for other baseline variables that are imbalanced, based on the analyses described in Section 11.1.1.

The comparison between treatments will also be conducted on the time to complete eschar removal measured from the date of ICF as an additional analysis.

As an additional analysis, time to complete eschar removal will be analyzed on a target wound level using a method of survival analysis with clustered data that is based on appropriate assumptions. By "clustered data", we refer to the multiple target wounds that can occur in a patient. The proportional hazards assumption will be checked in the same way as in the patient level analysis. I.e. a Cox regression model will be fitted with covariates treatment, center, age, %TBSA, proportion of the FT area of a patient, number of TWs (1,2,3-4, ≥5) and a variable representing the interaction between time since randomization and treatment group. The latter coefficient will be tested to be nonzero. Additionally, a log likelihood test comparing the model fit of a model with all time by covariate interactions added with a model without these interactions will be computed. The proportionality assumption will be rejected if one of these tests yields a significant result at the 10% level. If the proportional hazards assumption is appropriate we will use a marginal Cox regression analysis with a robust sandwich estimator. If not, then we will use a parametric frailty model. Either method can be implemented in SAS (see Gharibvand and Liu, 2009 for details). The marginal Cox regression model is implemented in the PHREG procedure and the robust variance option is implemented by specifying the COVS(AGGREGATE) option. This induces the use of the robust variance method of Binder et. al. [22]. The parametric frailty model will be implemented using the following SAS-code:

```
PROC PHREG DATA=burn_data;

CLASS Subject_id treatment_group centergroup numtw;

MODEL time*status(0) = treatment_group centergroup age tbsa pctFT numtw;

RANDOM Subject_id;

HAZARDRATIO "Frailty Model" treatment_group;

RUN;
```

where subject_ID is a unique identification number for each patient, time is the time to complete eschar removal on a wound level, status is an indicator whether the wound has achieved complete eschar removal or not (censoring indicator, 0 for censor and 1 for complete ER event), treatment_group gives the treatment group, centergroup is the stratification factor defined in Section 11.1.11, age is the patient's age, TBSA is the overall percent TBSA of a patient, pctFT is the proportion of the FT area of a patient, numtw is the number of TWs $(1,2,3-4, \ge 5)$ of the patient and burn_data is a SAS data set containing the required information. These methods include information on all the target wounds of each patient and account for any

within-patient correlation. Missing information due to incomplete follow-up is incorporated naturally into such analyses as censored observations.

Kaplan-Meier curves will be presented graphically to display the distribution of time to complete eschar removal (on a wound level) under the two treatments.

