9.1.1. Primary Endpoint: Time to Complete Eschar Removal

Estimated log hazard ratio from study MW2004-11-02 (SoC versus NexoBrid) = -1.39, using a Cox proportional hazards model with treatment as only covariate.

Standard error = 0.28

Target log hazard ratio = -1.39 + 0.28/2 = -1.25; target hazard ratio $\lambda = 0.29$.

The formula for the number of events D (successful complete eschar removals) is:

$$D = \frac{4(z_{\alpha} + z_{\beta})^2}{(\ln \lambda)^2}$$

(Piantadosi, Clinical Trials: A Methodologic Perspective, p.169)

 $z_{\alpha} = 1.96$;

 z_{β} = 1.28 for 90% power.

If the proportion of events in NexoBrid group is denoted by $p_1 = 0.59$

and the proportion of events in SoC group is denoted by $p_2 = 0.70$,

which are the observed proportions in the study MW2004-11-02, the number of patients required $n = \frac{2D}{p_1 + p_2} = 42$ (to the nearest even number), 21 in each group.

In accordance with the European regulatory requests and planned age distribution, we believe that a sample size of 80 patients per arm will detect with a 90% power a difference on the primary endpoint, which is well within what would be expected, based on the results from the previous study.

Based on the above calculations, we plan a study with total sample size of 160 patients; 80 (NexoBrid) + 80 (SoC)⁵.

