All variables not mentioned explicitly in the following will be analyzed descriptively (as part of the case-wise listing).

Unless otherwise specified, all statistical tests will be conducted against a two-sided alternative hypothesis, employing a significance level of 0.05.

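### Baseline covariates can displace the primary Cox test: either of two 10% proportionality checks, one of them a joint test mostly of nuisance terms, sends the analysis to a less powerful stratified Gehan test

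*SAP*

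**What the plan says.** SAP Section 11.1.3 makes a patient-level Cox regression the main test of time to complete eschar removal, adjusted for center, age, %TBSA, FT share and number of TWs. Section 11.1.8 groups centers into four regions for this purpose. Proportional hazards is checked twice: by the coefficient of treatment by time, and by "a log likelihood test comparing the model fit of a model with all time by covariate interactions added with a model without these interactions". The decision rule is "The proportionality assumption will be rejected if one of these tests yields a significant result at the 10% level". The consequence is "In this case, we will use a generalized Wilcoxon-Gehan test", coded in PROC LIFETEST with age group, FT group, number of TWs, TBSA group and center group all in the STRATA statement.

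Section 11.1.2 takes the main p-value from a re-randomization test. Section 9.1.1 sizes the trial on the Cox model and says that "a sample size of 80 patients per arm will detect with a 90% power a difference on the primary endpoint". Section 13.3 adds a second calculation: because proportional hazards was rejected in MW2010-03-02, it assumes the Wilcoxon-Gehan route and obtains 94 patients in total for 90% power. Enrollment closed at 145. The protocol synopsis names Cox regression for this endpoint and mentions no fallback. Section 11.1.5.1 applies the Section 11.1.3 procedure to the subject-level analysis of wound closure.

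**The concern.** The second check does not ask whether the treatment effect is proportional. It pools treatment with all the adjusting covariates, so a changing effect of region or wound count can remove the Cox test while the treatment hazard ratio is constant. Joining two 10% tests by an either-or rule also raises the chance of switching when nothing is wrong.

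Little is gained in return. The validity of the re-randomization p-value rests on the allocation procedure, not on proportional covariate hazards, and a non-proportional covariate can be handled within Cox by stratifying on it. At stake are which confirmatory test is reported, whether a hazard ratio is the main result, and some power on the endpoint that heads the hierarchy in Section 11.1.9.

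**Working it through.** **1. The plan's own figure.** Inputs from Section 9.1.1: "Target log hazard ratio = -1.39 + 0.28/2 = -1.25", z = 1.96, z = "1.28 for 90% power", event proportions 0.59 and 0.70.
- D = 4(1.96 + 1.28)² / 1.25² = 41.99 / 1.5625 = 26.9 events.
- n = 2 × 26.9 / (0.59 + 0.70) = 41.7, i.e. 42. The plan's figure is reproduced.

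**2. Both routes at 145 patients, on the documents' figures.**
- Cox: 145 × 0.645 = 93.5 events; at a hazard ratio of 0.29, power is above 99.9%.
- Gehan, scaling the 94 patients of Section 13.3: (1.96 + 1.28) × √(145/94) − 1.96 = 2.06, so power is about 98%.

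**3. Degrees of freedom of the joint test.** Treatment 1, region 3, age 1, %TBSA 1, FT share 1, number of TWs 3: total 10, of which 9 are not treatment.

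**4. Nominal false switching.** Two 10% tests joined by either-or give between 10% (complete overlap) and 1 − 0.9² = 19% (independence).

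**5. Simulated switching at N = 145.** The documents do not give the distributions of region, number of TWs, %TBSA or FT share, so these were assumed. Simulation 1 (1,500 trials per scenario) used whole-day times, regions 20/40/25/15%, number of TWs 45/30/17/8% and the age counts of Section 13.3. Simulation 2 (300-500 trials) used continuous exponential times and covariates without effect. The hazard ratio 3.45 is 1/0.29.

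| Scenario | Treatment × time | Joint | Either |
|---|---|---|---|
| Sim 1, HR 1, all proportional | 10.3% | 18.1% | 24.1% |
| Sim 1, HR 3.45, all proportional | 7.4% | 15.9% | 20.5% |
| Sim 1, HR 3.45, region Weibull shapes 1, 1, 1.6, 0.7 | 9.3% | 48.7% | 51.3% |
| Sim 2, HR 3.45, events 0.59/0.70, all proportional | 12.4% | 35.2% | 39.4% |
| Sim 2, HR 3.45, events 0.645 in both arms, all proportional | 12.0% | 28.3% | 34.3% |

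Two further simulations gave 17-23% and 21-27% with all hazards proportional, and 49-54% and 48-57% with region non-proportional. In Simulation 2 at N = 600 (80 trials only) the either-or rate was 20%, so the excess over the nominal range is largely a small-sample effect of the joint test. In the region scenario of Simulation 1, 51.3 − 9.3 = 42.0 points, or 82% of the switches, came from the joint test alone.

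**6. Simulated power (Simulation 1).**

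| Scenario | Cox always | Five-factor Gehan always | Rule as written | Treatment-only trigger |
|---|---|---|---|---|
| HR 3.45, all proportional | 99.7% | 77.5% | 94.5% | 97.0% |
| HR 3.45, strong region shapes | 99.5% | 74.9% | 85.2% | 95.7% |
| HR 2.0, all proportional | 79.2% | 35.4% | 68.7% | 74.2% |
| HR 2.0, strong region shapes | 79.4% | 37.3% | 56.7% | 75.1% |

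A weighted average confirms the order of size: 0.205 × 77.5 + 0.795 × 99.7 = 95.1%, and 0.513 × 74.9 + 0.487 × 99.5 = 86.9%. With milder region shapes (1, 1, 1.3, 0.8) the rule switched in 29% of trials and kept 91.5% power. A separate simulation (400 trials per scenario) gave 96% and 93% for the rule as written in the first two rows. A hazard ratio of 2.0 is not a design value in either document; it shows only what a smaller effect would cost.

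**7. Source of the loss.** The STRATA statement crosses 4 × 2 × 4 × 2 × 4 = 256 cells. At the target hazard ratio and N = 145, Simulation 2 gave 99.8% for the unstratified Gehan test. With the 256 cells it gave 88%, 77%, 62% and 47% as the assumed covariates went from concentrated to evenly spread; the share of patients in cells containing both arms fell from about 72% to 27%. Another check gave 95-96% when stratifying by region only.

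**Limits.** Simulation 1 used normal critical values in place of the 8,000 re-randomizations. Simulation 2 also used simple 1:1 allocation in place of minimization.

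**The case against.** The sponsor foresaw the switch. Section 13.3 assumes that proportional hazards will be rejected and sizes the Gehan route at 94 patients; with 145 enrolled, both routes exceed 90% on the documents' figures. The rule and its code are pre-specified, and no inflation of type I error has been shown; the Cox test kept its level (4.0-5.2%) at a hazard ratio of 1. Most of the power loss belongs to the fully crossed strata and would nearly vanish if they were coarsened. The false-switch rate also varies with assumptions. A valid p-value does not by itself make a hazard ratio interpretable when the model fits badly.

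All of this stands. It limits the size of the point but does not remove it: the coded fallback is the five-factor version, and the trigger decides how often it is used. Section 13.3 does not say whether its 94-patient simulation used those strata.

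Two stronger readings are tempting. A reader might infer that any single covariate that looks non-proportional discards the Cox test. The second check is one joint test, so the covariates act together, although one strong departure can be enough. A reader might also infer that power falls below the stated 90%. To get there, the fallback must keep less than 94/145 = 65% of the information assumed in Section 13.3. That is possible with sparse strata, but it rests on covariate spreads that the documents do not give.

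**Conclusion.** The point holds as a cheap improvement. As written, the rule gives up a sound Cox analysis in roughly 20-27% of trials of this size when every hazard is proportional (34-39% in one simulation), and in about half when region alone is strongly non-proportional. At the target hazard ratio, simulated power goes from about 100% to about 95% in the first case and to about 85-93% in the second. These sizes rest on assumed distributions of region, number of TWs, %TBSA and FT share, and on assumed region hazard shapes; the loss comes mainly from the sparse strata of the fallback. The documents do not support a claim that the trial misses its 90% power, nor one that the error rate is affected. What they do show is that nuisance covariates share in choosing the confirmatory test.

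**What to change.** In SAP Section 11.1.3:
- Let only the treatment-by-time interaction, at the 10% level, decide between Cox and Gehan.
- Report the joint time-by-covariate test descriptively.
- If a covariate is non-proportional, keep Cox as the main test and add a supportive Cox model stratified on that covariate, or with its time interaction.
- Apply the same trigger to the subject-level wound-closure analysis in Section 11.1.5.1, which refers to Section 11.1.3.

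It would also help to state in Section 13.3 whether the 94-patient simulation used the five-factor strata.

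The cost is about one sentence of SAP wording before database lock, and slightly less programming. The safeguard against a non-proportional treatment effect is kept, and the validity of the re-randomization p-value is untouched. The small downside is that covariate non-proportionality is dealt with in a supportive model rather than by changing the main test.
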